7.1.3. Adverse Events of Special Interest

An adverse event of special interest (AESI; serious or non-serious) is one of scientific and medical interest specific to the sponsor's product or program, for which ongoing monitoring and rapid communication by the investigator to the sponsor be appropriate. Such an event might warrant further investigation in order to characterize and understand it.

AESIs are defined in Section [7.3.4](#).

7.2. Evaluation of Adverse Events and Serious Adverse Events

The Investigator or designee is responsible for making an assessment as to the severity (CTCAE v5.0 Grade), causality/relationship to vidutolimod and cemiplimab separately, and outcome of AEs and SAEs (as defined in Section 7.2.3). Every attempt should be made to provide the causality/relationship at the time of reporting the SAE. In addition, the Investigator or designee must report any actions taken as a result of an AE or SAE separately for vidutolimod and cemiplimab.

7.2.1. Adverse Event Severity

For each recorded AE or SAE, the Investigator or designee must provide an assessment of Severity/Grade using the CTCAE v5.0 ([U.S. Department of Health and Human Services, 2017](#)). AE terms not found in the CTCAE v5.0 will be graded according to [Table 9](#).

Note that severity is not the same as “seriousness” (defined in Section 7.1.2). Seriousness (not severity) serves as a guide for defining regulatory reporting obligations.

ISRs will be graded as defined in [Table 4](#).

Worsening of an ongoing TEAE (i.e. an increase to higher grade) should be recorded as a new AE. Ongoing AEs that decrease in severity/grade should not be captured as new AEs.

Table 9: CTCAE Adverse Event Grades

Classification	Definition
Grade 1	Mild; asymptomatic or mild symptoms; clinical or diagnostic observations only; intervention not indicated
Grade 2	Moderate; minimal, local, or non-invasive intervention indicated; limiting age-appropriate instrumental activities of daily living
Grade 3	Severe or medically significant but not immediately life-threatening; hospitalization or prolongation of hospitalization indicated; disabling; limited self-care activities of daily living
Grade 4	Life-threatening consequences: urgent intervention indicated
Grade 5	Death related to adverse event

Reference: ([U.S. Department of Health and Human Services, 2017](#)).

Abbreviations: CTCAE = Common Terminology Criteria for Adverse Events.

7.2.2. Relationship to Study Drug

For each AE or SAE, the Investigator will determine whether there is a reasonable possibility demonstrated by evidence that suggests a causal relationship between the study treatment and each AE according to the categories provided below. Attribution of AEs will be determined for each of the individual components (vidutolimod and cemiplimab) of the study treatment. The Investigator may change their opinion of causality in light of follow-up information; if this occurs, the Investigator must amend the AE or SAE information in the EDC and on the paper SAE form accordingly.

Every AE must be assessed by the Investigator with regard to whether it is considered immune-mediated. For events that are potentially immune-mediated, additional information will be collected on the eCRF.

The following factors should be considered when assessing causality:

- Temporal relationship: time to onset vs time drug was administered
- Nature of the reactions: immediate vs. long term
- Clinical and pathological features of the events
- Existing information about the drug & same class of drugs
- Concomitant medications
- Underlying and concurrent illnesses
- Response to dechallenge (drug discontinuation) or dose interruption
- Response to rechallenge (re-introduction of the drug) or dose increase, when applicable
- Patient's medical and social history

Causality to the study drug (including study drug administration):

- Related:
 - The AE follows a reasonable temporal sequence from study drug administration and cannot be reasonably explained by the nature of the reaction, patient's clinical (eg, disease under study, concurrent diseases, concomitant medications), or other external factors.
- Or
- The AE follows a reasonable temporal sequence from study drug administration, and is a known reaction to the drug under study or its class of drugs or is predicted by known pharmacology.
- Not Related:
 - The AE does not follow a reasonable sequence from study drug administration or can be reasonably explained by the nature of the reaction, patient's clinical state (eg, disease under study, concurrent diseases, and concomitant medications) or other external factors.

Causality to the study conduct (protocol specified procedure):

- Related:
 - The AE follows a reasonable temporal sequence from a protocol specified procedure and cannot be reasonably explained by the nature of the reaction, patient's clinical (eg, disease under study, concurrent diseases, concomitant medications), or other external factors.
- Not Related:
 - The AE does not follow a reasonable sequence from a protocol specified procedure or can be reasonably explained by the nature of the reaction, patient's clinical state (eg, disease under study, concurrent diseases, and concomitant medications) or other external factors.

7.2.3. Classification of Adverse Event Outcome

AE outcome describes the status of the AE at the last observation. The Investigator will document the outcomes of each AE using the categories provided in below [Table 10](#).

Table 10: Classifications for Adverse Event Outcomes

Classification	Definition
Fatal	Termination of life as a result of an AE
Not recovered/not resolved	Subject has not recuperated, or the AE has not improved
Recovered/resolved	Subject has recuperated, the AE resolved, or returned to baseline status / stabilized
Recovered/resolved with sequelae	AE has resolved, but the subject has been left with symptoms or pathology
Unknown	Not known, not observed, not recorded, or refused

7.2.4. Action Taken Related to Study Drug Administration Regarding the Adverse Event

The Investigator will provide the action taken regarding study treatment separately for vidutolimod and cemiplimab in response to the AE. Refer to Section [4.1.1.4](#) and Section [4.1.2.2](#) for vidutolimod and cemiplimab allowed dose modifications. Classification for each of the potential actions taken are provided in [Table 11](#).

Table 11: Classifications for Actions Taken Related to Study Drug Administration Regarding an Adverse Event

Classification	Definition
No change	No change in administration of study drug
Study drug delayed	Temporary delay in administration of the study drug
Study drug withheld	One or more planned doses of study drug completely withheld (skipped)
Study drug permanently withdrawn	Administration of the study drug terminated (no further dosing)
Not applicable	Determination of a value is not relevant in the current context

7.3. Procedures for Recording and Reporting Adverse Events

7.3.1. Individual Case Safety Reporting (ICSR)

All events (serious and non-serious) must be reported with investigator's assessment of the event's seriousness, severity, and causality to the (when applicable, blinded) study drug. For SAEs and AESIs, a detailed narrative summarizing the course of the event, including its evaluation, treatment, and outcome should be provided on the AE CRF. Specific or estimated dates of event onset, treatment, and resolution should be included, when available. Medical history, concomitant medications, and laboratory data that are relevant to the event should also be summarized in the narrative. For fatal events, the narrative should state whether an autopsy was or will be performed

and include the results if available. Information not available at the time of the initial report must be documented in a follow-up report. Source documents (including hospital or medical records, diagnostic reports, etc.) will be summarized in the narrative on the AE CRF and retained at the study center and available upon request.

Urgent safety queries must be followed up and addressed promptly. Follow-up information and response to non-urgent safety queries should be combined for reporting to provide the most complete data possible within each follow-up.

Adverse events will be recorded from the time of informed consent until 100 days after the last dose of study drug (both vidutolimod and cemiplimab) or until an alternative anticancer treatment is initiated, whichever occurs first. AEs starting more than 100 days after the last dose of study drug should not be recorded on the AE eCRF unless they are considered to be related to study treatment. The date, time of onset, resolution, determination of seriousness, severity, action taken, outcome and relationship to vidutolimod and cemiplimab will be recorded for all AEs.

All AEs and SAEs experienced by a subject will be recorded on the appropriate eCRF. In addition, for all SAEs a paper SAE Report Form will be completed and submitted within 24 hours of awareness.

7.3.2. Reporting Serious Adverse Events

All SAEs and associated source documents must be reported in written or typed English via completion of the eCRF AE page and accompanying paper SAE Report Form (following the same reporting process outlined in Section 7.3) within 24 hours of first knowledge of the event regardless of relationship to the study procedures or individual study drugs. The paper SAE Report form should be used to record pertinent information, regarding the SAE. The Investigator is requested to supply as much detailed information as possible regarding the event at the time of the initial report.

SAEs will be collected from completion of the ICF until 100 days after the last dose of any study allowed drug treatment. SAEs starting more than 100 days after the last dose of study drug should not be recorded on the eCRF unless they are considered to be related to study treatment.

If at any time after the subject has completed participation in the study, the Investigator or study staff becomes aware of an SAE during the study reporting period that they believe is possibly, probably, or definitely related to either study drug (see Section 7.2.2), then the event and any known details must be reported promptly to the Sponsor or its representatives. The following reporting instructions must be followed.

At minimum, the Investigator will be asked to provide the following information:

- For the initial SAE notification, the Investigator must provide, at a minimum, basic information such as the protocol number, subject's year of birth or age at onset, subject identification number, period of study drug intake, event term, nature of the event, detailed description of the clinical course of the event, seriousness criteria, causality of the event to vidutolimod and cemiplimab separately, and severity.

- In addition, the initial SAE information entered on the eCRF and paper SAE Report Form should include all pertinent known information about the SAE and the affected subject, such as the following: subject sex; description of the AE including reason for assessment as serious, and individual study drug information including doses, dates of dosing, and action taken with individual study drugs.

Follow-up information must be entered or uploaded into the eCRF system and paper SAE Report Form (following the same reporting process outlined in Section 7.3.2) within 24 hours of the Investigator's first knowledge of the new information. Follow-up SAE reports may describe the evolution of the reported events and any new assessment of their outcome and/or relationship to individual study drugs. Supporting documentation may be solicited from the site even if the SAE occurred at another institution. Such documentation may include copies of relevant subject/hospital records, and pathology or autopsy reports. For subject deaths, the cause of death is to be recorded as the SAE term. A death certificate and an autopsy report, if performed, should be submitted.

The Sponsor designee contact information is available for SAE reporting on a 24-hour basis and is reviewed during normal business hours. A paper SAE Report Form should be completed and submitted within 24 hours of awareness.

7.3.3. Reporting Pregnancies

Female subjects or the partners of male subjects who become pregnant within 150 days of their last vidutolimod dose will be instructed to notify the Investigator immediately.

If the Investigator learns of a report of pregnancy at any time after the W1D1 visit up to 150 days after the last dose of the study drug, the Investigator must complete and submit a paper Pregnancy Report Form and report the pregnancy to Regeneron within 24 hours of awareness (following the same reporting process outlined in Section 7.3.2).

The Investigator will inform the subject that the Sponsor or its representatives is required to gather information regarding the course and outcome of a pregnancy that has occurred after exposure to a study drug. The progress of the pregnancy must be followed until the outcome of the pregnancy is known (i.e. delivery, elective termination, or spontaneous abortion). If the pregnancy results in the birth of a child, additional follow-up information may be requested.

The Investigator will be asked to obtain follow-up information no later than 2 months after the gestational period to obtain maternal/fetal/neonatal outcome and any other relevant information.

Follow-up information may be requested at additional time points. All study-related contacts involving a known pregnancy should include pregnancy status assessment until pregnancy outcome is known.

Please note that pregnancy in and of itself is not an AE or an SAE. Pregnancy should not be entered into the eCRF as an AE unless the Investigator suspects an interaction between the study drug and the contraceptive method. Additionally, all information received will be assessed for any AEs and SAEs and processed per study guidelines. If the subject is discontinued because of pregnancy, pregnancy will be documented as the reason for study discontinuation. Spontaneous abortions and stillbirths will be reported as SAEs.

7.3.4. Events that Require Expedited Reporting to Sponsor

The following events also require reporting to the sponsor (or designee) within 24 hours of learning of the event:

- **SAEs**
- **Selected Adverse Events of Special Interest** (AESIs; serious and nonserious). Adverse events of special interest for this study include the following:
 - Grade ≥ 2 Allergic /hypersensitivity reactions (cemiplimab and/or vidutolimod)
 - Grade ≥ 2 Injection site reactions (vidutolimod)
 - Grade ≥ 2 Infusion-related reactions (cemiplimab)
 - Grade ≥ 3 Hypotension (vidutolimod). Medical intervention beyond IV fluids indicated such as stress steroids (eg, 50 to 100 mg hydrocortisone orally or IV every 8 hours or equivalent, unless given prophylactically for adrenal insufficiency) or inpatient hospitalization
 - Grade ≥ 2 cytokine release syndrome (CRS, vidutolimod): Hypotension responding to fluids, and/or hypoxia responding to $<40\%$ O₂. NOTE: Administration of prophylactic fluids per Section 4.1.1.1 will not be considered Grade 2 CRS. Report Grade ≥ 2 CRS if subject requires intensification of IV fluid administration over baseline prophylaxis for management of hypotension.
 - Grade 3 or greater imAE or Grade 2 or greater uveitis
- **Pregnancy:** See Section 7.3.3

7.3.5. Notifying Health Authorities, IRBs/Ethics Committees, and Investigators

During the study, the sponsor and/or the contract research organization (CRO) will inform health authorities, IECs/IRBs, and the participating investigators of any SUSARs (suspected unexpected serious adverse reactions) occurring in other study centers or other studies of the active study drug (vidutolimod and cemiplimab) as appropriate per local reporting requirements. In addition, the sponsor and/or CRO will comply with any additional local safety reporting requirements. All notifications to investigators will contain only blinded information.

Upon receipt of the sponsor's notification of a SUSAR that occurred with the study drug, the investigator will inform the Institutional Review Board (IRB)/Ethics Committee (EC) unless delegated to the sponsor.

Expectedness of SAE for study drug (vidutolimod in combination with cemiplimab) is assessed against the Reference Safety Information (RSI) section of the current version of the Investigator's Brochure for vidutolimod that is effective for expedited safety reporting. Expectedness of SAE for cemiplimab is assessed against the current version of the cemiplimab Investigator's Brochure. Any SAE not listed as an expected event in the RSI section of the Investigator's Brochures or in the reference safety document (eg, USPI or SmPC) will be considered as unexpected. In addition, the sponsor will report all other SAEs to the health authorities, according to local regulations.

At the completion of the study, the sponsor will report all safety observations made during the conduct of the trial in the Clinical Study Report to health authorities and IECs/IRB as appropriate.

7.3.6. Follow-Up of Adverse Events/Serious Adverse Events

All AEs and SAEs documented at a previous visit that are designated as not recovered/resolved, will be reviewed by the Investigator at subsequent visits.

All AEs will be followed until resolution of AE, completion of the subject's study participation, or study termination, whichever occurs first.

SAEs and AEs resulting in discontinuation will be followed until 1 of the following occurs:

- The event resolves.
- The event stabilizes.
- The event returns to a baseline value if a baseline value is available.
- The event can be attributed to agents other than the study drug or to factors unrelated to study conduct.
- The Investigator and Medical Monitor agree that follow-up is no longer necessary.

Follow-up reports from the Investigator must be provided via completion of the eCRF AE page and accompanying paper SAE page within 24 hours of the Investigator's first knowledge of the new information. Additional information (i.e. hospital records, laboratory, or other diagnostic test results) should be provided if requested and/or indicated. In addition, for SAEs, the follow-up information should be added using the same form the initial SAE was reported on.

Rules for AE/SAE follow-up apply to all subjects, including those who withdraw consent prior to study completion (to the extent allowed). The Investigator will ensure that follow up includes further investigations to elucidate the nature and/or causality of the AE/SAE. These investigations must be consistent with appropriate medical management and subject consent.

Investigators are not obligated to actively seek AEs or SAEs in former study subjects that occur pursuant to the follow-up period. However, if the Investigator or designee learns of any AE or SAE at any time after a subject has been discharged from the study and the event is considered as reasonably related to the study drug, the Investigator will notify the Sponsor.

8. STATISTICAL METHODS

This section provides the basis for the statistical analysis plan (SAP) for the study. The SAP will be revised prior to the end of the study, to accommodate amendments to the clinical study protocol and to make changes to adapt to unexpected issues in study execution and data that may affect the planned analyses. The final SAP will be issued before the first database lock. Statistical analyses will be performed using SAS® software version 9.4 or higher.

8.1. Sample Size Justification

The study is conducted as an exploratory trial. Each cohort of A1, A2, B1, B2, C1, C2, D, E, and F, will enroll approximately 25 subjects. The total number of subjects to be enrolled into this study is approximately 225. Based on historical data, the ORR of available treatment for each disease in Cohort is listed in [Table 12](#). If the observed ORRs in these Cohorts A1, A2, B1, B2, C1, C2, D, E, and F are as listed in [Table 12](#), then the lower bound of 90% confidence interval of ORR is listed in the table below.

Table 12: ORR of Available Treatment by Cohort

Cohort	ORR of Available Treatment	Observed ORR ≥	Lower Bound of 90% Confidence Interval
A1	50%	72%	>50%
A2	<10%	24%	>10%
B1	50%	72%	>50%
B2	<10%	24%	>10%
C1	21%	40%	>21%
C2	<10%	24%	>10%
D	50%	72%	>50%
E	39%	60%	>39%
F	19%	40%	>21%

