1.3.3.4. Head and Neck (HPV-Positive)

HPV-positive OPSCC represents a distinct subset of HN cancer, at both the clinical and molecular levels ([Ferris, 2023](#)). In patients with oropharynx primary, HPV positivity can be established by a positive p16 immunohistochemistry (IHC) result. Alternatively, the presence of HPV E6/E7

mRNA transcripts in the tumor, as directly demonstrated by RNA ISH, can establish that an oropharynx SCC is HPV-positive ([Ferris, 2023](#)). A positive HPV DNA ISH result also establishes that an oropharynx primary tumor is HPV associated, although this test is less commonly used ([Gillison, 2016](#)). In HNSCC patients who present with cervical lymphadenopathy and occult primary, the diagnosis of HPV-associated disease with occult oropharynx primary is accepted when HPV positivity is documented by HPV RNA or DNA ISH ([NCCN, 2023](#)).

Patients with HPV-positive oropharynx squamous cell carcinoma (OPSCC) have lower risk of disease recurrence after curative intent therapy for locally advanced disease, compared to patients with HPV-negative oropharynx cancer ([Ang, 2010](#)). However, for patients who do experience recurrent or metastatic HPV-positive HNSCC and received pembrolizumab (either as monotherapy or in combination with chemotherapy), the median overall survival is less than 20 months ([Black, 2023](#)). Therefore, there is an urgent need for new treatment options for patients with R/M HPV-positive OPSCC.

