In a phase 2 study, HNSCC patients received pembrolizumab + SD-101, a TLR9 agonist of CpG-C class, in the 1L R/M setting. Overall, the objective response rate (ORR) was 24% for all HNSCC patients. Among patients with HPV-positive disease, ORR was 44% (7/16). Among patients with HPV-negative disease, ORR was 12% (2/17) ([Cohen, 2022](#)). These findings are consistent with results in a phase 2 study of pembrolizumab + vidutolimod in 1L R/M HNSCC patients, which enrolled 6 patients with HPV-positive R/M OPSCC. Among these 6 patients, there was one durable partial response, and one near-partial response (-29% reduction in target lesions by RECIST) (NCT04633278; Regeneron data on file). In these two studies, there was no signal for enhanced efficacy with the addition of TLR9 agonist to pembrolizumab in HPV-negative patients, compared with historical experience with pembrolizumab monotherapy in 1L R/M HNCC ([Burtness, 2019](#)). The mechanistic basis of potential enhanced efficacy of TLR9 agonist in HPV-positive OPSCC has not been established, but plasmacytoid dendritic cells (pDCs) from HPV-positive OPSCC tumors may secrete immune-supportive cytokines such as IFNAlpha, whereas pDCs from HPV-negative tumors may secrete immune-suppressive cytokines such as IL-10 and TNFAlpha ([Koucký, 2021](#)).

The current study will evaluate cemiplimab + vidutolimod in R/M, PD-L1 CPS score ≥ 1 , HPV-positive OPSCC among patients who have not received prior systemic therapy for R/M disease.

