8.6.1. Confirmed Objective Response Rate

The primary efficacy endpoint for the study is the confirmed ORR based on RECIST v1.1 as determined by the Investigator.

The confirmed ORR is defined as the proportion of the subjects in the Safety Analysis Set who have confirmed best response as CR or PR. The confirmed ORR will be calculated as the number of subjects with a confirmed CR or PR divided by the number of subjects in the analysis population [ORR = (CR + PR)/number of subjects] for the Safety Analysis Set per cohort. For the ORR, 95% Clopper-Pearson confidence intervals will be calculated.

Subjects who discontinue due to death as a result of disease progression, or disease progression prior to having a post-baseline tumor assessment will be classified as having a best response of

PD. Subjects who discontinue prior to having a post-baseline scan for other reasons will be counted as non-responders.

The primary efficacy analysis of confirmed ORR will be assessed according to RECIST v 1.1 by the Investigator for the Safety Analysis Set.

The primary analysis will be performed for each cohort and no multiplicity adjustment will be made since separate inferences will be drawn for each cohort.

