**Table 1: ORR of Available Treatment by Cohort**

Cohort	ORR of Available Treatment	Observed ORR $\geq$	Lower Bound of 90% Confidence Interval
A1	50%	72%	>50%
A2	<10%	24%	>10%
B1	50%	72%	>50%
B2	<10%	24%	>10%
C1	21%	40%	>21%
C2	<10%	24%	>10%
D	50%	72%	>50%
E	39%	60%	>39%
F	19%	40%	>21%

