### 7.2. Analysis of Efficacy Data

#### 7.2.1. Analysis of Primary Efficacy Endpoint

For each cohort, the ORR per RECIST 1.1 will be summarized using FAS, along with 95% exact confidence interval using Clopper-Pearson method.

To determine the consistency of treatment effect across various demographics and baseline subgroups, the ORR (with a nominal 95% confidence interval [CI]) may be estimated within each category of the following subgroup variables: age, gender, race, ECOG, prior therapy.

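### Cohort F's planning row (19% / 40% / >21%) is out of line with the other eight rows: its last two cells match a 21% reference, not the printed 19%

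*Protocol*

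**What the plan says.** Protocol 8.1 states that each of the nine cohorts "will enroll approximately 25 subjects". It then gives, by cohort, a historical ORR for available treatment and an observed ORR, and says that if the observed ORR is as listed, "then the lower bound of 90% confidence interval of ORR is listed in the table below". SAP 2.2 repeats this under "Table 1: ORR of Available Treatment by Cohort". The two tables carry the same values:

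| Cohorts | ORR of available treatment | Observed ORR ≥ | 90% lower bound |
|---|---|---|---|
| A1, B1, D | 50% | 72% | >50% |
| A2, B2, C2 | <10% | 24% | >10% |
| C1 | 21% | 40% | >21% |
| E | 39% | 60% | >39% |
| F | 19% | 40% | >21% |

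Neither document names the method behind the 90% interval. For the analysis, Protocol 8.6.1 says that "95% Clopper-Pearson confidence intervals will be calculated", and SAP 7.2.1 reports the ORR "along with 95% exact confidence interval using Clopper-Pearson method".

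The Cohort F rationale (Protocol 1.3.3.4) describes outcomes on pembrolizumab through survival ("the median overall survival is less than 20 months"). It also makes a comparison with past results ("compared with historical experience with pembrolizumab monotherapy in 1L R/M HNCC"). It gives response rates for combinations with a TLR9 agonist, but none for available treatment.

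**The concern.** The table is there to show which observed ORR would put the lower confidence bound above the ORR of available treatment. Eight rows do so by repeating their reference in the last column (reading <10% as 10%). Row F instead shows clearance of 21%, which is not its stated reference, and its last two cells are identical to those of C1. A reader cannot tell whether the first cell is wrong or the last two were carried over from C1.

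This table is the only sample-size justification for the primary endpoint, so what is in doubt is the benchmark against which Cohort F's result will be read. An observed 9/25 would clear 19% but not 21% on the table's 90% basis.

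**Working it through.** **Inputs.** n = 25 per cohort (Protocol 8.1, stated as approximate). Confidence level 90% (Protocol 8.1, SAP 2.2), taken as two-sided, so 5% in the lower tail. Method assumed to be Clopper-Pearson, which both documents name for the 95% analysis interval. References and observed ORRs are from Protocol Table 12 and SAP Table 1.

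**Formula.** For x responses in n, the lower bound L(x) is the 0.05 quantile of a Beta(x, n − x + 1) distribution. For each reference, find the smallest x with L(x) above it.

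**Step 1: reproduce the other eight rows (n = 25).**

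| Reference | Smallest x clearing it | Bound | One response fewer | Table lists |
|---|---|---|---|---|
| 50% | 18 (72%) | 53.8% | 17: 49.6% | 72% |
| 10% | 6 (24%) | 11.0% | 5: 8.2% | 24% |
| 21% | 10 (40%) | 23.6% | 9: 20.2% | 40% |
| 39% | 15 (60%) | 41.7% | 14: 37.9% | 60% |

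All eight rows come out as printed.

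**Step 2: check that this depends on the method.** Smallest counts for references 50%, 10%, 21% and 39%, where the table needs 18, 6, 10 and 15:

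- Clopper-Pearson: 18, 6, 10, 15
- Wilson: 17, 5, 9, 14
- Normal approximation: 17, 7, 10, 14
- Agresti-Coull: 17, 6, 9, 14
- Jeffreys: 17, 6, 9, 14

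Of these five, only Clopper-Pearson fits. Wilson with continuity correction, tried as a sixth, also gives 18, 6, 10 and 15.

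**Step 3: apply the same basis to row F.**

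- Reference 19%: 8/25 has bound 17.0% and 9/25 has bound 20.2%. The smallest count is 9, so the row would read 19% / 36% / >19%. Continuity-corrected Wilson also gives 9.
- Reference 21%: 9/25 has bound 20.2% and 10/25 has bound 23.6%. The smallest count is 10, so the row would read 21% / 40% / >21%.
- 40% is therefore the minimal listed value only for references from 20.2% up to, but not including, 23.6%. 21% lies in that range and 19% does not.

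**Step 4: sensitivity to cohort size.** Because 25 is approximate, the smallest counts for the two references are:

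| n | 23 | 24 | 25 | 26 | 27 |
|---|---|---|---|---|---|
| Reference 19% | 9 | 9 | 9 | 9 | 10 |
| Reference 21% | 9 | 9 | 10 | 10 | 10 |

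The references separate by one response at n = 25 and 26 and coincide at 23, 24 and 27.

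**The case against.** Nothing printed in row F is false. At 10/25 the 90% bound is 23.6%, which exceeds both 21% and 19%, so an observed 40% would exclude the stated reference. Neither document says that the last column must repeat the reference, or that the observed ORR is the smallest that clears it. That rule is inferred, and it rests on four distinct patterns rather than eight independent rows. A planner may list a value one response above the minimum. This stands, and it is why the point is an inconsistency rather than a false statement.

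Row F might also have been worked out on a 95% interval: there 9/25 gives 18.0% and 10/25 gives 21.1%, so 19% / 40% / >21% would fit. That cannot be ruled out as the origin. But the column is labelled 90%, and 95% bounds fail elsewhere in the table: 6/25 gives 9.4% against 10%, and 15/25 gives 38.7% against 39%. Row F would still be on a different basis from its neighbours.

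Finally, little depends on the cell. The trial is described as exploratory, SAP 1.2 states that there is no formal hypothesis, and no decision rule cites the table. The protocol synopsis mentions hypothesis testing of the ORR but gives no null value. This limits the weight of the point but does not remove the mismatch.

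**Conclusion.** The concern holds as a minor inconsistency, in identical form in both documents. Row F is the only one of nine rows whose lower-bound cell does not match its own reference. On the basis that reproduces the other eight rows, its 40% and >21% go with a 21% reference. The size is two percentage points in the reference, or one response at n = 25 (9/25 = 36% against 10/25 = 40%).

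The visible mismatch needs no assumption beyond reading <10% as 10%. The 36%-against-40% result assumes n = 25, a two-sided 90% Clopper-Pearson interval, and the inferred smallest-count rule. The documents do not show which cell is off, and the effect is confined to Cohort F's planning benchmark.

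**What to change.** The sponsor should confirm the reference ORR for Cohort F, give its source, and align the row in Protocol Table 12 and SAP Table 1.

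- **If 21% was intended:** print 21% / 40% / >21%.
- **If 19% stands:** change the last cell to >19%. Then either keep 40% (90% bound 23.6%, 95% bound 21.1%), which alters one cell, or list 36% (90% bound 20.2%) to follow the other rows. If 36% is listed, note that 9/25 does not clear 19% on the 95% interval that will be reported (18.0%).

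In either case, add a footnote giving the interval method and n. 90% Clopper-Pearson with n = 25 fits the other rows, but the sponsor should confirm it. The cost is one or two cells and a footnote per document, with no change to sample size or analysis. Protocol section 8 already foresees a SAP revision before the end of the study, which could carry the SAP correction.
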